^c Ozanimod titration will occur during the first 7 days of study intervention exposure, per label (Table 7.1-2). Participants will receive a phone call on Day 5 (when titrating their dose from 0.23 mg to 0.46 mg) and again on Day 8 (when titrating their dose from 0.46 mg to 0.92 mg) as a reminder about the dose adjustment. If required, an unscheduled visit can be planned anytime during the treatment period. Data regarding study procedures conducted at such unscheduled visits (eg, blood, stool, and urine tests; safety assessments) will be documented in the EDC tool.

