7.1 Study Interventions Administered

Details of the IP used for both cohorts are provided in Table 7.1-1:

Table 7.1-1: Study Interventions

	Study Intervention Details (for Cohort 1 and Cohort 2)
Intervention Name	Ozanimod (Zeposia)
Type	Drug
Dose Formulation	Capsule
Unit Dose Strength(s)	0.23 mg, 0.46 mg, and 0.92 mg
Dosage Level(s)	Days 1–4: 1 × 0.23 mg (QD) Days 5–7: 1 × 0.46 mg (QD) Day 8 and thereafter : 1 × 0.92 mg (QD)
Route of Administration	Oral
Use	Active
Sourcing	Provided by the Sponsor
Packaging and Labeling	Ozanimod will be packaged and labelled per country requirements.
Current/Former Name(s) or Alias(es)	RPC1063, BMS-986374

Table 7.1-2Participants will receive a phone call on Day 5 (when titrating their dose from 0.23 mg to 0.46 mg) and again on Day 8 (when titrating their dose from 0.46 mg to 0.92 mg) as a reminder about the dose adjustment (see [Table 2-1](#)).

Table 7.1-2: Ozanimod Dose Titration Regimen

Days	Regimen
Days 1–4	0.23 mg QD PO
Days 5–7	0.46 mg QD PO
Day 8 and thereafter	0.92 mg QD PO

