 - ALT or AST > $3 \times \text{ULN}$ with the appearance of fatigue, nausea, vomiting, right upper quadrant pain or tenderness, fever, rash, and/or eosinophilia (> 5%).

Refer to the SOA for the data that will be collected at the time of treatment discontinuation and follow-up and for any further evaluations that can be completed.

All participants who discontinue study intervention should comply with the protocol-specified follow-up procedures, as outlined in [Section 2](#). The only exception to this requirement is when a participant withdraws consent for all study procedures, including post-treatment study follow-up, or loses the ability to consent freely (eg, is imprisoned or involuntarily incarcerated for the treatment of either a psychiatric or physical illness).

If study intervention is discontinued prior to the participant's completion of the study, the reason for the discontinuation must be documented in the participant's medical records, per local regulatory requirements in each region/country, as applicable, and entered on the appropriate eCRF page.

8.1.1 *Treatment Interruption*

Participants should be instructed that if they forget to take a dose, they can take it within 4 hours of the normal dosing time; otherwise, they should take their next dose at the regular time on the following day. If the participant vomits the dose, he/she should be instructed not to take another dose on the same day, but to take the next dose at the regular time on the following day. Participants will record whether they took the daily dose of medication in an electronic diary that will be reviewed periodically by the site staff and the site monitor.

If a dose is missed during the first 2 weeks of treatment, re-initiate treatment using dose escalation regimen. If a dose of study intervention is missed after the first 2 weeks of treatment, continue with the treatment as planned. If more than 7 consecutive days between Day 15 and Day 28 of treatment, or more than 14 consecutive days after Day 28 of treatment, re-initiate treatment using the dose escalation regimen. The Medical Monitor should be contacted to discuss completing the dose escalation schedule.

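### Section 8.1.1's missed-dose instruction to participants has no first-2-weeks exception, so the re-escalation rule may not be applied in time after a miss on Days 9–14

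*Combined protocol and SAP*

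**What the plan says.** Section 8.1.1 (Treatment Interruption) has two relevant paragraphs.

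The first sets out what participants are to be told. A forgotten dose may be taken within 4 hours of the usual time; "otherwise, they should take their next dose at the regular time on the following day". After vomiting a dose, they are not to take another that day, "but to take the next dose at the regular time on the following day". Neither instruction is limited to particular treatment days, and neither asks the participant to contact the site. Daily dosing is recorded in an "electronic diary that will be reviewed periodically by the site staff and the site monitor".

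The second paragraph makes the treatment day decisive: "If a dose is missed during the first 2 weeks of treatment, re-initiate treatment using dose escalation regimen". A single dose missed after the first 2 weeks does not interrupt the planned treatment. The paragraph ends: "The Medical Monitor should be contacted to discuss completing the dose escalation schedule".

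The regimen to be restarted is in Section 7.1 ("Table 7.1-2: Ozanimod Dose Titration Regimen"): 0.23 mg on Days 1–4, 0.46 mg on Days 5–7, and 0.92 mg from Day 8. The Figure 5.1-1 footnotes in Section 5.1 provide for calls on Day 5 and "again on Day 8 (when titrating their dose from 0.46 mg to 0.92 mg) as a reminder about the dose adjustment". The same footnote adds: "If required, an unscheduled visit can be planned anytime during the treatment period". In Table 2-1, the next visit after Day 1 is Week 4 (Day 28, window 7 days either side).

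**The concern.** The participant instruction fits only the branch of the rule that applies after the first 2 weeks, yet it is given for all days. In the first 2 weeks one missed dose is meant to trigger a full restart of the titration. The participant decides what to swallow the next morning, so the rule works as intended only if the participant knows of it, or if the site learns of the miss almost at once. Section 8.1.1 gives the participant neither the exception nor a reason to call.

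Days 9–14 are the weak spot. They lie after the Day 8 call, which is the last scheduled contact, and before the Week 4 visit. What is at stake is adherence to a dosing rule that the sponsor itself chose for early treatment.

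**Working it through.** The plan gives no figure on this point to reproduce. The check is a reading of the two paragraphs against the schedule, followed by day counts.

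**Inputs**
- Restart rule: a dose missed on Days 1–14 leads to re-escalation (Section 8.1.1).
- Re-escalation length: 4 days at 0.23 mg plus 3 days at 0.46 mg = 7 days (Table 7.1-2).
- Planned dose on Days 9–14: 0.92 mg (Table 7.1-2).
- Scheduled contacts after Day 1: calls on Days 5 and 8, then the Week 4 visit on Day 28 ± 7 = Day 21 to 35 (Table 2-1 and its footnote on titration).
- Table 2-1 marks diary-compliance review on Day 1 and then at Week 4. Review of compliance with study drug first appears at Week 4. Both are also marked in the unscheduled column.

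**Exposure to the gap.** Days 9–14 are 6 of the first 14 doses: 6/14 = 43%. This is a share of calendar days, not a rate of missed doses.

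**Next dose after a miss.** Continuing as planned gives 0.92 mg and the rule gives 0.23 mg: 0.92/0.23 = 4 times.

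**Timing.** For a miss on Day d, re-escalation should run from Day d+1 to Day d+7. The delay to the Week 4 visit runs from 21 − d to 35 − d days.

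| Missed dose (Day) | Re-escalation (Days) | Delay to Week 4 visit (days) |
|---|---|---|
| 9 | 10–16 | 12–26 |
| 10 | 11–17 | 11–25 |
| 11 | 12–18 | 10–24 |
| 12 | 13–19 | 9–23 |
| 13 | 14–20 | 8–22 |
| 14 | 15–21 | 7–21 |

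Overall the delay is 7 to 26 days. The visit falls inside the re-escalation window in only one case: a Day 14 miss with the visit held on Day 21, which is the last day of that window. In every other case the window has already closed. A participant who simply continued would then have taken all 4 + 3 = 7 re-escalation doses at 0.92 mg. That participant reached 0.92 mg on Day 8, so this departs from the rule but is not a new peak dose.

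**Timing of a backstop review.** A review on Day 14 can precede that day's dose, its 4-hour grace period or its diary entry, and so can overlook a Day 14 miss. A review on Day 15 covers all six days, with a delay of 15 − d, that is 1 day (Day 14) to 6 days (Day 9).

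**The case against.** The strongest reply is that the safety rule is there, in the very next paragraph. Both paragraphs are addressed to sites, which do the instructing, and a site that reads the whole section has what it needs. The first paragraph fixes when the next dose is taken and the second fixes the regimen. That the participant continues at the planned strength is an inference, since no strength is named. Participant materials are not among the documents and may say more.

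There are also real safeguards. Participants are trained on the diary at screening. Rectal bleeding and stool frequency are recorded daily for the first 12 weeks, so the diary is in regular use at the time that matters. Periodic review is not confined to scheduled visits. The unscheduled column of Table 2-1 covers diary review, drug compliance and dispensing. The Medical Monitor is to be contacted about the escalation.

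Much of this stands, and it limits the point. A reader might infer that the two paragraphs contradict each other; they do not, strictly. A reader might take 7 to 26 days as the expected delay; it is the worst case, with no periodic review and no unscheduled contact. A reader might infer harm to participants; the documents quantify no clinical consequence of one missed day. A reader might count a vomited dose as missed; the section treats vomiting separately and does not say, so this is a clarification and not a second defect.

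What the reply does not remove is that no safeguard is tied to a missed dose. The periodic review has no stated interval or alert, and the calls are described only as dose-adjustment reminders. The Medical Monitor sentence does not say how the site would learn of the miss.

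**Conclusion.** The point holds as a minor patient-safety wording issue. Followed as written on Days 9–14, the participant instruction would ordinarily lead to 0.92 mg the next day where the section's own rule restarts at 0.23 mg. The only scheduled contact that could reveal this comes 7 to 26 days after the miss, usually too late for the restart to be applied as intended.

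This rests on three assumptions: that a participant told only to take the next dose takes the planned strength; that participant materials do not already add the exception; and, for the 7 to 26 days, that no review or contact comes sooner. The number of participants affected cannot be estimated from the documents. Primary and secondary endpoints, analysis sets and statistical methods are unaffected.

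**What to change.** Add to the participant instruction in Section 8.1.1, and carry into participant materials, a sentence such as: *If you miss a dose in the first 2 weeks, contact the site before taking the next dose, because the escalation must be restarted.* State also what the participant should do if the site cannot be reached.

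As a backstop, time one of the periodic electronic diary reviews that the section already requires to Day 15, not Day 14. Any miss found then should be discussed with the Medical Monitor. After a Day 9 miss the participant may already have taken five further doses at 0.92 mg (Days 10–14), and the protocol does not say whether to restart at that stage.

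Optionally, state whether a vomited dose counts as missed for the restart rule.

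The cost is a few sentences and a fixed date for one existing review. The downside is slightly more site contact in the first 2 weeks. No new visit or procedure is needed.

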8.1.2 Post-study Intervention Study Follow-up

Participants who discontinue study intervention may continue to be followed.

8.2 Discontinuation From the Study

Participants who request to discontinue study intervention will remain in the study and must continue to be followed for the protocol-specified follow-up procedures. The only exception to this is when a participant specifically withdraws consent for any further contact with him/her or persons previously authorized by the participant to provide this information.

- Participants should notify the investigator of the decision to withdraw consent from future follow-up.
- The investigator should explain the withdrawal of consent in detail in the medical records, including whether the withdrawal is from further treatment with study intervention only or whether it is also from study procedures and/or post-treatment study follow-up, and should enter this on the appropriate eCRF page.
- In the event that vital status (whether the participant is alive or dead) is being measured, publicly available information should be used to determine vital status only as appropriately directed in accordance with local law.
- If the participant withdraws consent for disclosure of future information, the Sponsor may retain and continue to use any data collected before such a withdrawal of consent.

8.2.1 Individual Discontinuation Criteria

- A participant may withdraw completely from the study at any time at his/her own request, or may be withdrawn at any time at the discretion of the investigator for safety, behavioral, compliance, or administrative reasons; this is expected to be uncommon. Stopping study intervention is not considered withdrawal from the study.
- At the time of discontinuing from the study, the end of treatment and follow-up visits should be conducted, if possible, as shown in the SOA. See the SOA ([Table 2-1](#) and [Table 2-2](#)) for the data to be collected at the time of study discontinuation and follow-up and for any further evaluations that need to be completed.
- The participant will be permanently discontinued both from the study intervention and from the study at that time.
- If the participant withdraws consent for disclosure of future information, the Sponsor may retain and continue to use any data collected before such a withdrawal of consent.

8.3 Lost to Follow-up

The following actions must be taken if a participant fails to return to the clinic for a required study visit:

- All reasonable efforts must be made to locate the participant to determine and report their ongoing status. This includes follow-up with persons authorized by the participant.
- Lost to follow-up is defined by the inability to reach the participant after a minimum of **three (3)** documented phone calls, faxes, or emails, as well as a lack of response by the participant to one (1) registered mail letter. All attempts should be documented in the participant's medical records.
- If it is determined that the participant has died, the site will use permissible local methods to obtain the date and cause of death.
- If the investigator's use of a third-party representative to assist in the follow-up portion of the study has been included in the participant's informed consent, then the investigator may use a Sponsor-retained third-party representative to assist site staff with obtaining the participant's contact information or other public vital status data necessary to complete the follow-up portion of the study.
- The site staff and representative will consult publicly available sources, such as public health registries and databases, in order to obtain updated contact information.
- If, after all attempts, the participant remains lost to follow-up, then the last known alive date, as determined by the investigator, should be reported and documented in the participant's medical records.

9 STUDY ASSESSMENTS AND PROCEDURES

- Study procedures and timing are summarized in the SOA ([Section 2](#)).
- Protocol waivers or exemptions are not allowed.
- All immediate safety concerns must be discussed with the Sponsor immediately upon occurrence or awareness to determine if the participant should continue or discontinue treatment.
- Adherence to the study design requirements, including those specified in the SOA ([Section 2](#)), is essential and required for study conduct.
- All screening evaluations must be completed and reviewed to confirm that potential participants meet all eligibility criteria before study intervention administration on Day 1. The investigator will maintain a screening log to record details of all participants screened and to confirm eligibility or record reasons for screening failure, as applicable.
- Procedures that are conducted as part of the participant's routine clinical management (eg, blood count) and obtained before signing of informed consent may be utilized for screening or baseline purposes, provided the procedure meets the protocol-defined criteria and has been performed within the timeframe defined in the SOA ([Section 2](#)).

9.1 Efficacy Assessments

9.1.1 Efficacy Assessments for the Study

Study evaluations will take place in accordance with the SOA (Section 2). Endoscopy- and biopsy-related procedure details will be provided to the sites in a separate document/manual. A brief description about additional efficacy assessments is provided in Sections 5.1 and 5.4.

9.1.2 Other Efficacy Assessments for the Study

9.1.2.1 Histology Assessment

A histology assessment will be done using the Geboes score. This instrument has been used to characterize the histological appearance of the mucosa in registrational UC studies.³²

9.1.2.2 Health-related Quality of Life

HRQOL will be captured using the following questionnaires: [REDACTED] IBDQ, [REDACTED].

[REDACTED] The IBDQ was developed to measure the patient's experience of inflammatory bowel diseases (UC and CD). It consists of 32 questions divided into 4 dimensions: bowel symptoms (10 items), systemic symptoms (5 items), emotional function (12 items), and social function (5 items). Each question ranges from 1 "worst situation" to 7 "best situation"; and the total score ranges from 32 to 224, with higher scores representing better QOL.^{34,35} [REDACTED]

The timing of HRQOL collection is provided in the SOA (Section 2).

9.2 Adverse Events

The definitions of an AE or an SAE can be found in APPENDIX 5.

AEs will be reported by the participants

The investigator and any qualified designees are responsible for detecting, documenting, and reporting events that meet the definition of an AE or SAE and remain responsible for following up on AEs that are serious, considered related to the study intervention or the study, or that caused the participant to discontinue before completing the study.

Refer to [APPENDIX 5](#) for SAE reporting.

9.2.1 Time Period and Frequency for Collecting AE and SAE Information

The collection of nonserious AE and coronavirus disease (COVID) AE information should begin at screening until the follow-up visit, at the time points specified in the SOA ([Section 2](#)).

All SAEs must be collected from the time of signing the ICF, including those thought to be associated with protocol-specified procedures, and within 30 days following discontinuation of dosing.

The investigator must report any SAE that occurs after these time periods and that is believed to be related to study intervention or a protocol-specified procedure (eg, endoscopy, biopsy).

- Medical occurrences that begin before the start of study intervention but after obtaining informed consent will be recorded in the appropriate section of the eCRF.
- All SAEs will be recorded and reported to the Sponsor or designee within 24 hours, as indicated in [APPENDIX 5](#).
- The investigator will submit any updated SAE data to the Sponsor or designee within 24 hours of the updated information being available.

Investigators are not obligated to actively seek AEs or SAEs in former study participants. However, if the investigator learns of any SAE, including a death, at any time after a participant has been discharged from the study, and he/she considers the event to be reasonably related to the study intervention or study participation, the investigator must promptly notify the Sponsor.

The method of evaluating and assessing causality of AEs and SAEs, and the procedures for completing and reporting/transmitting SAE reports are provided in [APPENDIX 5](#).

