^e WOCBP only. Pregnancy test anytime within 7 days prior to day of study intervention initiation is permissible – if pregnancy test is done locally, it must be documented.

^f Optional test of FSH level may be used to exclude childbearing potential in peri-menopausal females.

^g For all biologics, the washout period is 8 weeks or 5 elimination half lives, which ever is shorter, but it may be waived with the demonstration of absent drug levels on TDM assay.

ⁱ Stool PCR panel may be performed as an alternative to stool culture if that is in routine clinical use at a site.

^j Endoscopy- and biopsy-related procedure details will be provided to the sites in a separate document/manual.

^k A brief description about additional efficacy assessments is provided in [Section 9.1](#).

^l Only for Cohort 1.

^m Only for Cohort 2.

ⁿ A brief description about HRQOL assessments is provided in [Section 9.1.2.2](#).

^o A brief description about healthcare resource utilization assessments is provided in [Section 9.10](#).

^p Ozanimod titration will occur during the first 7 days of study intervention exposure, per label ([Table 7.1-2](#)). Participants will receive a phone call on Day 5 (when titrating their dose from 0.23 mg to 0.46 mg) and again on Day 8 (when titrating their dose from 0.46 mg to 0.92 mg) as a reminder about the dose adjustment.

Table 2-2: Schedule of Activities for Year 2 (IM047029)

Procedure	Week 104 EOT/ET ^a (Day 728)	Week 116 PTFU (Day 812)	Unscheduled ^b	Notes
Visit Window (± n Days)	14	14		
Concomitant Medications	X	X		Assess for change in concomitant medications (see Section 7.7)
UC Medications	X	X		
Tobacco / e-cigarette vape use	X	X		Assess for change in use
Physical Examination				See Section 9.5.1 for details
Weight	X	X		
Vital Signs (HR, BP, Temperature [°C])	X	X		
Complete Physical Examination	X			
Interim Physical Examination		X		
Electronic Diary (eCOA)				
Site Review of Electronic Daily Diary Compliance	X	X	X	
Blood and Urine Tests^c				See Section 9.5.4 for details
CBC and Differential Count	X		X	
Biochemistry ^d	X		X	

Table 2-2: Schedule of Activities for Year 2 (IM047029)

Procedure	Week 104 EOT/ET ^a (Day 728)	Week 116 PTFU (Day 812)	Unscheduled ^b	Notes
Visit Window (± n Days)	14	14		
Additional Efficacy Assessments^e				
PGA Collection	X	X		Physician-reported
RB Subscore	X	X		
SF Subscore	X	X		Recorded for 7 days prior to each study visit
HRQOL^f				
IBDQ	X	X		
Healthcare Resource Utilization^g				
AE Reporting				

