10.5 Interim Analyses

Pre-planned interim analyses may be performed when all participants in both cohorts have completed the primary endpoint visit (ie, Week 12 for Cohort 1 and Week 26 for Cohort 2), and again when all participants in both cohorts have completed the 52-week visit. The final study analysis will be performed when all participants have completed the 116-week study (including the safety follow-up visit) or discontinued early from the study. Additionally, optional datacuts at other time points will be planned, if required. Details of all planned analyses will be provided in the SAP.

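### The protocol conflicts on when all-cause SAE collection ends: 30 days after dosing (Section 9.2.1) or the Week 116 follow-up visit (Table 2-2)

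*Combined protocol and SAP*

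**What the plan says.** Section 9.2.1 sets two collection periods and a residual duty.

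- Non-serious and COVID AEs: "information should begin at screening until the follow-up visit", at the schedule's time points.
- All SAEs: from signing of consent "and within 30 days following discontinuation of dosing".
- Afterwards, the investigator still "must report any SAE that occurs after these time periods and that is believed to be related to study intervention or a protocol-specified procedure".

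Three other places bear on the same question.

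- Table 2-2 places the next scheduled visit after Week 104 (Day 728) at "Week 116 PTFU (Day 812"), each with a window of 14 days either side. The SAE monitoring row is marked at Week 116 exactly as the AE monitoring row is, with no footnote on relatedness. Section 10.5 treats this as the safety visit, timing the final analysis for when all participants have "completed the 116-week study (including the safety follow-up visit") or have discontinued early.
- Section 9 makes adherence to the Schedule of Activities a requirement.
- Appendix 5, on reporting SAEs to the sponsor, applies to SAEs regardless of their relation to study intervention and gives no end date.

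Table 4-3 makes the number and proportion of participants with AEs, and with SAEs, a secondary endpoint for both cohorts. Section 10.4.6 says when an event starts to count as treatment-emergent but not when it stops.

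**The concern.** A longer collection period for non-serious than for serious events is the reverse of what one would expect, and the protocol gives no reason for it. Under Section 9.2.1 alone, a non-serious AE on Day 800 is collected, while an event that is serious from onset and judged unrelated falls outside the stated period. Section 9.2.3 adds an oddity: a non-serious AE that later becomes serious is to be reported as an SAE.

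Two things are at stake. First, the AE and SAE proportions in the secondary endpoint could rest on different observation periods. Because every SAE is also an AE, the overall AE proportion would itself mix the two. Second, after day 30 the only filter would be the causality judgement of an unblinded investigator (Section 7.3), in a study with no control group (Section 10.1) and no data monitoring committee (Section 5.1.1).

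The protocol does treat the time after dosing as relevant beyond 30 days. Table 3.3.1-1 lists immune effects after stopping as a risk, Section 6.3 sets a 90-day contraception period after stopping, and Table 7.7-1 advises avoiding live vaccines for up to 3 months.

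If sites resolve the conflict differently, what they record at Week 116 will also differ between sites.

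**Working it through.** **Inputs.** Week 104 = Day 728, Week 116 = Day 812 and a window of 14 days either side at both visits (Table 2-2); all-cause SAE period of 30 days after dosing stops (Section 9.2.1). Assumption: the last dose is taken on the day of the Week 104 visit.

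**Reproducing the schedule.** 104 × 7 = 728 and 116 × 7 = 812, as stated. Nominal follow-up is 812 − 728 = 84 days.

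**Disputed period, nominal.** The Section 9.2.1 period ends on Day 728 + 30 = 758. What remains is Days 759-812, or 812 − 758 = 54 days.

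- Share of follow-up: 54/84 = 64.3%.
- Share of the whole schedule: 54/812 = 6.7%.

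**With visit windows.** Disputed days = follow-up day − last-dose day − 30.

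| Case | Last dose | Follow-up visit | Disputed days | Share of follow-up | Share of schedule |
|---|---|---|---|---|---|
| Shortest | 728 + 14 = 742 | 812 − 14 = 798 | 798 − 742 − 30 = 26 | 26/56 = 46.4% | 26/798 = 3.3% |
| Nominal | 728 | 812 | 54 | 54/84 = 64.3% | 54/812 = 6.7% |
| Longest | 728 − 14 = 714 | 812 + 14 = 826 | 826 − 714 − 30 = 82 | 82/112 = 73.2% | 82/826 = 9.9% |

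**Is an unrelated SAE on Day 790 in scope?**

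| Source | Answer |
|---|---|
| Section 9.2.1, SAE period | No: Day 790 is after Day 758 and the event is not considered related |
| Table 2-2, Week 116 SAE monitoring | Apparently yes: no relatedness limit is stated |
| Section 9 | The schedule must be followed |
| Appendix 5, SAE reporting | Yes on its face: relatedness is irrelevant and no end date is given |

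**After the proposed change.** With all SAEs collected to the follow-up visit, the disputed period falls from 54 days to 0.

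These are days, not events. The documents give no SAE rate for the weeks after dosing, so the number of SAEs affected cannot be calculated.

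**The case against.** The strongest objection is that nothing need be lost. A reader who sees only Section 9.2.1 might infer that unrelated SAEs in Days 759-812 need not be collected. The documents as a whole do not support that: Table 2-2 schedules the check, Section 9 makes the schedule binding, and Appendix 5 requires reporting whatever the relatedness. This stands, and it is why the point is a conflict and not an established gap in collection.

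It does not settle the matter, though. Section 9.2.1 is the section that sets the collection period, whereas Appendix 5 deals with how and how fast to report. The Week 116 mark could also serve a 30-day rule, since no visit is scheduled between Weeks 104 and 116. No text says which is meant.

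Section 9.2.1 is itself open to other readings. The residual duty begins after periods named in the plural, which could include the one ending at the follow-up visit. Serious COVID events may be covered by the COVID wording. Both add to the ambiguity.

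A reader might also infer a far longer gap for participants who stop treatment early. Section 8.2 says those who ask to stop "will remain in the study and must continue to be followed for the protocol-specified follow-up procedures", and Section 8.2.1 adds: "Stopping study intervention is not considered withdrawal from the study". But Section 8.1.2 says only: "Participants who discontinue study intervention may continue to be followed". Table 2-2 provides end-of-treatment and follow-up visits for participants who leave the study prematurely, and no day is fixed for an early stopper's follow-up visit. Any figure for that group would rest on an assumption the documents do not support, so none is given.

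On weight, three mitigating facts stand. Related SAEs remain reportable throughout; the summaries are descriptive, with no hypothesis test (Section 10.1); and Section 10.4 defers detailed methods to the SAP. No SAP text beyond the protocol's own statistical section is in the supplied document, and it may set a common cut-off. A cut-off would align the summaries, but it could not restore events that sites had not recorded.

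**Conclusion.** The point holds as an inconsistency to be reconciled. Section 9.2.1 ends all-cause SAE collection 30 days after dosing; Table 2-2, Section 9 and Appendix 5 point to collection through Week 116. The period in doubt is nominally 54 of 84 follow-up days, ranging from 26 to 82, for a completer whose last dose is at the Week 104 visit. Against the whole schedule it is 6.7% nominally.

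If sites follow Section 9.2.1 alone, the SAE proportion has a shorter observation period than the non-serious AE proportion within the same secondary safety endpoint. Loss of events is possible, not certain, and its extent cannot be derived. Severity is minor to moderate; the correction is worth making because it is cheap.

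**What to change.** Amend Section 9.2.1 so that all SAEs, regardless of causality, are collected from consent through the post-treatment follow-up visit. This matches the non-serious AE period and the SAE check already marked in Table 2-2. Keep the duty to report related SAEs after that visit. For early stoppers, state which visit ends the period. In Section 10.4.6, give one common end point for the AE and SAE summaries, and carry it into the SAP.

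The alternative is a footnote limiting the Week 116 check to the Section 9.2.1 scope. That would tell sites what to do, but it would leave the two periods unequal and Appendix 5 without an end date.

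The cost is a wording change and a few more SAE reports to process. The visit and the SAE check are already scheduled.
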